## **2.15.2 Childhood Health Assessment Questionnaire (CHAQ) for subjects with Psoriatic Arthritis**

The Childhood Health Assessment Questionnaire CHAQ© ([Singh et al 1994; Ruperto et al 2001](#)), will be used to assess physical ability and functional status of patients as well as quality of life, for those children only who have reported History of Psoriatic Arthritis. The disability dimension consists of 20 multiple choice items concerning difficulty in performing eight common activities of daily living; dressing and grooming, arising, eating, walking, reaching, personal hygiene, gripping and other “activities”. The person completing the questionnaire (parent/custodian) chooses from four response categories, ranging from ‘without any difficulty’ to ‘unable to do’.

Descriptive statistics will be used to summarize responses on the CHAQ© Questionnaire by treatment, total score and by domain. In case of low number of subjects with completed CHAQ questionnaire, summary statistics of CHAQ and VAS will not be provided.

### **Parent's or patient's global assessment of patient's overall well-being (VAS)**

The parent's or patient's global assessment of patient's overall well-being will be assessed on the VAS that is part of the CHAQ©. The VAS scale ranges from 0-100 mm, from very well (0 mm) to very poor (100 mm). Scores on the 100-mm linear scale will be measured to the nearest millimeter from the left.

### **Parent's or patient's assessment of pain (VAS)**

The parent's or patient's assessment of pain will be assessed on the VAS that is part of the CHAQ©. The VAS scale ranges from 0-100 mm, from no pain (0 mm) to very severe pain (100 mm). Scores on the 100-mm linear scale will be measured to the nearest millimeter from the left.

For parent's or patient's global assessment of patient's overall well-being and of pain (VAS score) summary statistics for the observed values and the change/percent change from baseline will be provided by visit.

## **2.15.3 Biomarkers**

Not applicable.

## **2.15.4 Other Exploratory analyses**

Not applicable.

## **2.15.5 Interim analysis**

[figure not shown]
Apart from the final analysis, the study is also planned with two full analyses.

The first full analysis will be performed when all patients completed the Week 24 visit. And the next full analysis will be performed when all patients completed the Week 52 visit (i.e. Maintenance period).

The data cut-off date for the Week 24 PEA is the date of the last Week 24 visit for study subjects, i.e. 7 March 2019. The Week 24 PEA will include all efficacy data up to week 24

visit for each individual subject. For inclusion of safety data, we apply individual data cut-off of each subject to maximize use of available data. Thus for each subject, we will include all safety data collected until the last visit of the subject prior to the PEA data cut-off of 7 March 2019.

The data cut-off date for the Week 52 interim analysis is the date of the last Week 52 visit for study subjects, i.e. 18 September 2019. The Week 52 interim analysis will include all efficacy data up to week 52 visit for each individual subject. For inclusion of safety data, we apply individual data cut-off of each subject to maximize use of available data. Thus for each subject, we will include all safety data collected until the last visit of the subject prior to the interim analysis data cut-off of 18 September 2019.

### 3 Sample size calculation

Approximately 160 pediatric subjects from 6 to less than 18 years of age, with 2 subgroups: 6 to less than 12 years of age, and 12 to less than 18 years of age. Stratification is planned for age (<12 years,  $\geq$ 12 years) and weight (<25kg, 25-<50kg and  $\geq$ 50kg). It will be targeted to have at least 30 subjects in the <12 years subgroup at a minimum. Enrollment of children aged 6 to less than 12 years will proceed after efficacy and safety data for approximately 80 (approximately 40 treated with AIN) enrolled adolescents (aged 12 to less than 18 years) treated for 28 weeks have been reviewed and deemed satisfactory by a Data Monitoring Committee.

Since two secukinumab dose regimens will be tested versus placebo with respect to the coprimary endpoints (PASI 75 response and IGA 0 or 1 response at Week 12), the type-I-error will be split to 1.25% one-sided for each comparison. With 40 subjects per group and assuming a response rate of 10% for PASI 75 response and IGA 0 or 1 response in the placebo group, the power to show a response rate of 65% for PASI 75 response and 45% for IGA 0 response in the secukinumab groups based on Fisher's exact test (nQuery Advisor 7.0, two group Fisher's-exact test of equal proportions) is approximately 99% for PASI 75 response and approximately 88% for IGA mod 2011 0 or 1 response. For the secondary endpoint of PASI 90 response at week 12, assuming a response rate of 8% in the placebo group, the power to show a significant difference between a secukinumab dose and placebo, assuming a response rate of 39% in the secukinumab groups based on Fisher's exact test (nQuery Advisor 7.0, two group Fisher's-exact test of equal proportions) is approximately 82% for PASI 90 response. The assumed response rates for secukinumab are based on the confirmatory efficacy in severe patients in the adult phase III program. At Week 12, PASI 75 response rates of 11% and PASI 90 response rates of 7% have been reported in the placebo group in [Paller et al \(2008\)](#) for children and adolescents aged 4-17 years.

## 4 Change to protocol specified analyses

Following are the changes to protocol specific analysis:

Protocol amendment 3 included the plan for an additional Interim Analysis prior to the Week 24 PEA analysis, once sufficient safety [REDACTED] data had been collected. This analysis aligned with the efficacy extrapolation principle, was expected to provide the basis for a submission package to health authorities (HA), with the intent to allow earlier availability of secukinumab to pediatric patients in countries which accept a submission of clinical data with use of extrapolation methodology. However, due to the acceleration of patient recruitment in the months following the amendment, Novartis concluded that this analysis would no longer bring a considerable time gain for earlier submission. Thus this additional analysis was not performed and the submission of pediatric data will occur according to the initial plan based on the Week 24 PEA.

The following analyses have been removed from the analysis plan:

- The maximum change (maximum decrease and maximum increase) from baseline within treatment period for each laboratory parameter
- The stratified Van- Elteren testing and Hodges-Lehmann estimates for the absolute value and the percentage change from baseline of CDLQI total score.
- “Pure non-responder” imputation will be used, instead of “Modified non-responder” imputation for missing data, as a sensitivity analysis in efficacy analyses.

### 4.1 Additional and data driven analysis

In addition to the planned analyses, the following additional analyses will be performed after the database lock of the Week 24 analysis.

#### Analyses using extended visit window for Week 12

Sensitivity analysis with extended Week 12 analysis visit window using MI and pure non-responder imputation for missing data will be performed (Week 12 visit window day 72-102, instead of day 72-88). Number and percentage of subjects with PASI 50, PASI 75, PASI 90, PASI 100 and IGA 0 or 1 response at Week 12 will be summarized. Moreover, an exact logistic regression will be fitted to compare AIN457 low and high dose groups to the controls. This additional analysis was driven by the review of data post Week 24 DBL. As a number of patients, delayed beyond Day 88 their Week 12 CRF visit, this analysis was done to have a better understanding of the impact of these delays.

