#### 2.1.1.5 Visit windows

[figure not shown]
Visit-windows will be used for the data that is summarized by visit; these are based on the study evaluation schedule and comprise a set of days around the nominal visit day. For any assessment, there are the protocol defined scheduled visits around which visit windows were created to cover the complete range of days within the study. The visit windows are shown in [Table 2-2a](#) [REDACTED], which apply to measurements taken at every visit. For assessments collected less often, different visit windows will be applied as detailed below. When visit windows are used, all visits will be re-aligned, i.e., they will be mapped into one of the visit windows. E.g., if the Week 4 visit of a subject is delayed and occurs on Day 46 instead of on Day 29, say, then it will be re-aligned to visit window Week 8. In the case of major deviations from the visit schedule, or due to unscheduled visits, several assessments of a subject may fall in a particular visit window (either scheduled or unscheduled). Statistical approaches to handle multiple assessments in a given visit window are specified below. Of note, subjects are allowed to have gaps in visits.

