| Week 236 (EOT)     | 236 | 1653 | Day 1640-1667 |
| Week 240 (F4)      | 240 | 1681 | Day 1668-1695 |
| Week 244 (F8)      | 244 | 1709 | Day 1696-1723 |
| Week 248 (F12)     | 248 | 1737 | Day 1724-1751 |
| Week 252 (F16 EOF) | 252 | 1765 | Day 1752-1779 |

EOI: End of Induction Period; EOM: End of Maintenance Period; EOT: End of Treatment; EOF: End of Follow-up

For parameters, which are not collected at every visit (e.g. weight), visit windows defined in the tables above will be combined. E.g., if a parameter is measured at Week 12 and Week 24 only, then Week 12 visit window will extend from Day 2 to Day 88 (combining Week 1 to Week 12 visit windows), Week 24 will extend from Day 89 to Day 183 (combining Week 13 to Week 24). If more than one assessment falls into the interval, then the rules defined in [Section 2.1.1.6](#) are applied.

Maintenance period visits will not be mapped into induction period, and induction period visits will not be mapped into maintenance period. For example, if a subject is coming late for the Week 12 visit (induction period), and the visit would fall into the Week 13 (maintenance period) visit window, then it would not be mapped to maintenance period for the analysis but will still be considered as part of induction period. Of note, for subjects who discontinue in induction/maintenance period, i.e. not moving into maintenance/extension period, measurements taken in follow-up period would still be considered for induction/maintenance period.

In addition, sensitivity analyses for PASI and IGA mod 2011 0/1 response parameters will be performed based on extended Week 12 visit window from Day 72 to Day 102. See [Section 4.1](#) for details.

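### Does the Day 88 limit of the Week 12 window wrongly remove late pre-dose visits from the co-primary analysis?

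*SAP*

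**What the plan says.** SAP section 2.1.1.5 says that "visit windows were created to cover the complete range of days within the study" and that "all visits will be re-aligned, i.e., they will be mapped into one of the visit windows". Its example moves a Week 4 visit made on Day 46 into the Week 8 window, so study day decides the window, not the nominal visit.

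Table 2-2a puts Week 12 at Day 85 with a window of Day 72 to 88. Week 13 runs from Day 89 to 95 and Week 14 from Day 96 to 102.

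The text below the table separates the periods. "Maintenance period visits will not be mapped into induction period", and the reverse is also barred. For a subject who comes late to Week 12 and lands in the Week 13 window, "it would not be mapped to maintenance period for the analysis but will still be considered as part of induction period". For subjects who discontinue, "measurements taken in follow-up period would still be considered for induction/maintenance period". The same text announces that sensitivity analyses of the PASI and IGA responses "will be performed based on extended Week 12 visit window from Day 72 to Day 102".

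Section 4.1 repeats this as "Week 12 visit window day 72-102, instead of day 72-88", under multiple imputation and under pure non-responder imputation, with exact logistic regression against the controls. It labels the analysis as driven by data review after the Week 24 lock and gives the reason: "As a number of patients, delayed beyond Day 88 their Week 12 CRF visit, this analysis was done to have a better understanding".

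**The concern.** Taken together, these statements seem to contradict each other for a pre-dose Week 12 visit on, say, Day 90. By the table it is Week 13. By the period rule it may not go to maintenance. By the general rule it must have a window. Week 12 is the last induction window, so it is the only slot left. Section 4.1 points the other way: studying the impact of the delays has little purpose if those visits already counted as Week 12.

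The co-primary data are at stake. Protocol section 3.1 asks for the endpoint assessment before the Week 12 dose, and a late pre-dose value meets that. If it is left out and no other value lies in Day 72 to 88, it is replaced by imputation draws in the primary analysis. In the sensitivity analysis (SAP section 2.6.4) it becomes a non-response. The variable list in the imputation code of SAP section 5.1.2.3 stops at the primary endpoint week, so the late value would not inform its own imputation. The site meanwhile reports PASI 75 status from that visit to the IRT (protocol section 6.4.2), so the status acted on and the status analysed could differ.

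**Working it through.** **1. Is the Day 88 limit odd?** Days allowed after the target day in Table 2-2a:

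- Week 8: 71 − 57 = 14
- Week 12: 88 − 85 = 3
- Week 20: 155 − 141 = 14
- Week 24: 183 − 169 = 14
- Week 1: 11 − 8 = 3; Week 2: 18 − 15 = 3; Week 3: 25 − 22 = 3
- Week 13: 95 − 92 = 3; Week 14: 102 − 99 = 3; Week 15: 109 − 106 = 3

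These windows close at the midpoint between adjacent target days, rounded down: (57 + 85)/2 = 71; (85 + 92)/2 = 88.5, giving 88; (113 + 141)/2 = 127. Three days is what the rule gives wherever the next visit is a week away. The extended window allows 102 − 85 = 17 days.

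**2. Can the passages be read together?** The late-visit sentence names a period (induction), not an analysis visit. Table 2-2a assigns analysis visits by study day. On that reading the Day 90 value is an induction record outside the endpoint window, which fits section 4.1. Only the general statement that all visits are mapped resists, and the late-visit sentence is the more specific one. This is an inference; no sentence states it.

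**3. The plan's own figures.** SAP section 3 gives 40 per group, one-sided 1.25%, Fisher's exact test. Exact enumeration gives:

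| Endpoint | Rates | Stated | Recomputed |
|---|---|---|---|
| PASI 75 | 65% vs 10% | about 99% | 99.9% |
| IGA 0 or 1 | 45% vs 10% | about 88% | 88.4% |
| PASI 90 | 39% vs 8% | about 82% | 82.1% |

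**4. Scale under non-responder scoring.** Assume k of 40 late, with lateness unrelated to response. One late responder scored as non-response moves an arm's rate by 1/40 = 2.5 points. The expected IGA difference (planned 45 − 10 = 35 points) becomes:

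| Late in | Formula | k = 1 | k = 2 | k = 4 |
|---|---|---|---|---|
| Both arms | 35 × (1 − k/40) | 34.13 | 33.25 | 31.50 |
| Secukinumab only | 45 × (1 − k/40) − 10 | 33.88 | 32.75 | 30.50 |
| Placebo only | 45 − 10 × (1 − k/40) | 35.25 | 35.50 | 36.00 |

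With both arms late, exact power for k = 1, 2, 4 is 86.9%, 85.4%, 81.9% for IGA and 80.4%, 78.5%, 74.5% for PASI 90. PASI 75 stays above 99%. These figures concern the non-responder method, not the primary analysis.

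**5. What would a clarification change?** There are two cases. If the locked Week 24 programs left late visits out, the Day 72 to 88 result governs H1 to H6 and the Day 72 to 102 result stands beside it, as section 4.1 already plans. If they included late visits, that locked result governs. In neither case does a hypothesis test change.

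**The case for a change.** The strongest case for acting is that the co-primary data set should not rest on an unstated mapping. Section 4.1 shows that late visits did occur. A late pre-dose value precedes both the placebo switch and the dosing errors at Weeks 13 to 15, so it is clean endpoint information. The period rule already keeps Week 12 and Week 13 visits apart, so the Day 88 limit is not needed for that. Section 4.1 also does not repeat that only pre-dose induction assessments qualify for the wider window, and it specifies no count of late visits by arm.

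Much of this stands as a comment on wording. It does not support a new rule. Counting late visits up to Day 102 would still discard a pre-dose visit on Day 105, so the same objection returns at a later day. Day 102 was itself chosen after lock: the SAP Document History dates it to 06-Aug-2019. By protocol section 5.4, designated sponsor staff are unblinded after the Week 24 lock, so making that mapping primary would invite more doubt than it removes. The visit-window text had been revised on 24-Apr-2019, before lock.

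The IRT point is weaker than it looks. That status routes placebo subjects at Week 12, and nothing requires it to equal the windowed analysis value. Nor does the protocol leave timing open: section 6 asks for the designated day or as near as possible, and Table 6-1 puts Week 12 at Day 85.

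**Conclusion.** The SAP does not state which analysis visit a pre-dose Week 12 visit after Day 88 receives. Section 4.1 implies, without saying so, that such values were outside the main Week 12 analysis. This is a missing detail and calls for no change to the analysis. The window follows the table's own midpoint rule, the passages can be read coherently, and the obvious alternative is already specified for all the PASI responses and IGA 0 or 1 under both imputation methods. The locked result keeps governing H1 to H6 and the passing of alpha. What remains is for the study report: which mapping the locked programs used, and how many visits came after Day 88 in each arm.

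Size and direction are unknown, because the number late and their arms are not given. The differences and power figures above rest on assumed counts, equal response in late and timely subjects, and non-responder scoring. No effect on the multiple-imputation analysis has been shown. Part of the sentence introducing the windows is redacted, and the etanercept window table (Table 2-2b) is not in the text available, though neither is likely to affect the placebo comparisons.

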#### Analyses by IRT dosing error

In this study, an Interactive Response Technology (IRT) error led to additional dosing of some subjects. The dosing errors happened after the primary endpoint (Week 12) assessment. Specifically, 36 patients who were assigned to the low dose and high dose secukinumab groups were dispensed active medication at Week 13, 14, 15 visits. At these visits, the patients who were randomized to active treatment groups were expected to receive placebo medication as to maintain the blind.

Analyses will be performed for the below groups of IRT error affected and not affected patients to understand the impact of overdosing caused due to the error, by using MI and pure non-responder imputation for missing data:

- AIN457 Low dose Affected
- AIN457 Low dose Not Affected
- AIN457 High dose Affected
- AIN457 High dose Not Affected

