## 2.6.4 Handling of missing values/censoring/discontinuations

The following imputation methods will apply to the missing data for analysis up to Week 52 including primary W12 analysis:

- Response variables based on PASI score and IGA mod 2011 categories will be imputed with multiple imputations (MI) method as primary imputation method. Multiple imputation (MI) is a simulation based approach where missing values are replaced by multiple Bayesian draws from the conditional distribution of missing data given the observed data and covariates, creating multiple completed data sets. These completed data sets can then be analyzed using standard methods. Within this analysis, the PASI score or

IGA mod 2011 categories will be imputed and response variables will be derived based on the imputed scores. In the multiple imputation analysis, the response status will be imputed based on the individual treatment arm information.

- (Pure) Non-responder imputation will be used as a sensitivity method: Missing values with respect to response variables based on PASI score and IGA mod 2011 categories will be imputed with non-response regardless to the reason for missing data. Subjects with missing baseline or those with all post-baseline missing will be imputed with non-response.

[REDACTED]

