### **Analyses by IRT dosing error**

Additional analysis will be performed for the treatment emergent adverse events on or after Week 13 visit and up to Day 365, by IRT dosing error, by primary system organ class and preferred term. See [Section 4.1](#) for details.

Adverse events that occurred from Week 13 up to Day 365 since randomization for subjects affected by IRT dosing error will be listed.

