#### **Analyses by IRT dosing error, body weight and dose group**

Analyses will be performed for IRT error affected and not affected patients within the groups by body weight and secukinumab dose. The treatment groups will be:

- AIN457 75 mg and 25-<50 kg Not affected
- AIN457 150 mg and 25-<50 kg Affected
- AIN457 150 mg and 25-<50 kg Not affected
- AIN457 150 mg and  $\geq$ 50 kg Affected
- AIN457 150 mg and  $\geq$ 50 kg Not affected
- AIN457 300 mg and  $\geq$ 50 kg Affected
- AIN457 300 mg and  $\geq$ 50 kg Not affected

For PASI 50, PASI 75, PASI 90, PASI 100 and IGA 0 or 1 response, the missing data will be imputed by pure non-responder imputation method.

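### The IRT-error comparison sets no Week 13 entry condition for the Not affected group, so early leavers can lower its response rates under non-responder imputation and its crude AE rates

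*SAP*

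**What the plan says.** SAP 4.1 reports the event: "Specifically, 36 patients who were assigned to the low dose and high dose secukinumab groups were dispensed active medication at Week 13, 14, 15 visits". The planned medication at those visits was placebo, to keep the blind. The comparison is then set up: "Analyses will be performed for the below groups of IRT error affected and not affected patients to understand the impact of overdosing". The groups are Affected and Not affected within low dose and within high dose. The same sentence goes on to name two missing-data methods: "caused due to the error, by using MI and pure non-responder imputation for missing data".

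A second set of tables splits further: "Analyses will be performed for IRT error affected and not affected patients within the groups by body weight and secukinumab dose". For response there, "the missing data will be imputed by pure non-responder imputation method", with no multiple-imputation version.

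For safety, SAP 2.9.1 adds a table of "treatment emergent adverse events on or after Week 13 visit and up to Day 365, by IRT dosing error". It names no denominator. SAP 2.9 makes the safety set the default for all safety analyses.

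The imputation rules are in SAP 2.6.4. Under pure non-responder imputation, missing responses "will be imputed with non-response regardless to the reason for missing data". Under multiple imputation the rule differs: "In the multiple imputation analysis, the response status will be imputed based on the individual treatment arm information".

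The analysis sets in SAP 2.2 have no Week 13 condition. The full analysis set is every child in the randomized set with treatment assigned. The safety set is everyone with at least one dose. None of these sections says who belongs to Not affected.

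**The concern.** The two groups have different entry conditions. To be Affected a child must still be on treatment at Weeks 13 to 15. To be Not affected, as the text stands, it is enough not to be among the 36. A child who stopped in induction could never have met the error, yet has no other group to fall into. This is an immortal-time problem.

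Both consequences point the same way. Leavers lower the Not affected response rate when missing counts as failure. They also lower the Not affected crude AE rate, because they are barely observed in the window. A real effect of three extra active doses would plausibly raise response and AEs in Affected, so the artefact resembles the effect being looked for. SAP 5.1.2.2 also plans exact logistic regression for the IRT-error subjects under both imputation methods, so under non-responder imputation the artefact can enter formal odds ratios as well as descriptive tables.

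**Working it through.** **Plan's own figures.** The IRT comparison carries no stated figure beyond the count of 36. The response rates used below come from SAP 3 (65% PASI 75, 45% IGA 0 or 1). Its power statements were reproduced by exact enumeration of Fisher's test (40 per group, one-sided 1.25%): 99.9%, 88.4% and 82.1%, against about 99%, 88% and 82% stated.

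**Inputs.**
- Planned total about 160, allocated 1:1:1:1 (SAP 1.1): 160 × 2/4 = 80 on secukinumab from randomization.
- Affected: 36. Not affected: 80 − 36 = 44. These are planned counts with the two doses pooled; the dose split of the 36 is not given.
- k = secukinumab children who left before Week 13. Not given, so assumed between 0 and 8 of 80 (0 to 10%).
- p = rate among children who reached Week 13, taken as equal in both groups (no effect of the extra doses). The SAP's Week 12 planning rates serve as illustration.

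**Response under non-responder imputation.** Protocol 3.1 sends induction leavers to follow-up instead of maintenance, and SAP 2.1.1.5 keeps their follow-up measurements in the induction period. They therefore have no maintenance data and count as failures at every later visit. Expected rates are p in Affected and p × (44 − k)/44 in Not affected, so the gap is p × k/44.

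| k | Not affected, p = 65% | Gap (points) | Not affected, p = 45% | Gap (points) |
|---|---|---|---|---|
| 0 | 65.0% | 0 | 45.0% | 0 |
| 2 | 62.0% | 3.0 | 43.0% | 2.0 |
| 4 | 59.1% | 5.9 | 40.9% | 4.1 |
| 8 | 53.2% | 11.8 | 36.8% | 8.2 |

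Example: 65% × 40/44 = 59.1%; 65.0 − 59.1 = 5.9.

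**False signal.** In 4,000 simulated comparisons with no effect and p = 65%, a one-sided 2.5% Fisher test favoured Affected in 1.1% (k = 0), 2.9% (k = 2), 4.3% (k = 4) and 11.6% (k = 8) of runs. The SAP does not specify this test for the comparison; it is a yardstick.

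**Adverse events.** SAP 5.1.3.1 defines crude incidence as x/n, and SAP 2.9.1 ends treatment-emergent cover 84 days after the last dose. The window from Day 92 (scheduled Week 13) to Day 365 has 365 − 92 + 1 = 274 days. An induction leaver last dosed on Day 1 is covered to Day 85, which gives 0 days in the window. One last dosed on Day 57 (Week 8) is covered to Day 141, which gives 141 − 92 + 1 = 50 days. Such a child counts fully in n and hardly at all in x. If no event is counted for leavers and the true rate is 60% (assumed), the gap is 60% × k/44: 2.7 points at k = 2, 5.5 at k = 4 and 10.9 at k = 8. These are upper limits, because some events can fall in the covered days.

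**Multiple imputation.** Leavers' scores are drawn within the treatment arm and not set to failure, so p × k/44 does not apply.

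**With a Week 13 entry condition.** Denominators become 36 and 44 − k. Both expected rates equal p, and the gap is 0 for every k.

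**The case against.** The SAP nowhere says that early leavers belong to Not affected. A reader might infer that it places them there by design, but that follows only from the missing definition combined with the default sets. SAP 4.1 introduces the groups straight after describing what should have been given at the Week 13 to 15 visits, and the AE table starts at the Week 13 visit. A programmer could reasonably restrict both groups to children seen then, and no bias would follow. This stands as a limit on the claim. It does not replace a definition.

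A reader might also infer that every response result in this comparison is distorted. The documents do not support that: the main affected/not-affected comparison is run with multiple imputation as well, and a divergence between the two methods would point to the artefact. However, the split by body weight and dose, the version that holds weight category fixed, uses non-responder imputation only.

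The SAP plans other outputs: response with error-affected results set to missing, figures by age stratum without affected subjects, and listings of Week 13 to 15 doses and of AEs in affected children. Conclusions need not rest on this comparison alone, but none of these outputs repairs it.

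Finally, the analysis is labelled data-driven, and the errors came after the Week 12 assessment, so no confirmatory hypothesis is touched. The artefact would exaggerate an effect of the extra doses on AEs and would not hide one. Both points are right and limit the severity.

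**Conclusion.** The point holds in a limited form. With the analysis sets and imputation rules as written, induction leavers can enter only Not affected. This biases the non-responder-imputed response tables and the crude AE tables in one direction, towards an apparent effect of the extra doses. The multiple-imputation response analysis is free of this mechanical gap.

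The size is unknown, because the documents do not give k. With planned counts and a 65% response it is zero at k = 0 and about 3, 6 and 12 points at k = 2, 4 and 8. It would differ with the actual counts and within the separate dose and weight groups.

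A reader might go further and call the comparison uninterpretable. That is too strong: the bias may be nil or small, and one of the two response methods avoids it. Nor would an entry condition make the comparison fair. The SAP's list of weight-by-dose groups contains no Affected group at 75 mg, so Affected children in the low-dose arm appear to be only those of at least 50 kg, while Not affected includes lighter ones. Weight, and with it probably age, still differs between the groups.

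**What to change.** In SAP 4.1 and 2.9.1, define both groups among children randomized to secukinumab who received study medication at the Week 13, 14 or 15 visits:
- Affected: dispensed active drug at any of these visits.
- Not affected: dispensed only the planned placebo at these visits.

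Use these denominators for all IRT-error response and AE tables, including the split by body weight and dose. List by dose arm the children who left earlier, so that k is visible. Describe the comparison as non-randomized and state the weight difference in the low-dose arm.

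The cost is a short definition, a subset flag and a rerun of these tables. The downside is a smaller Not affected group, 44 − k instead of 44 on planned counts.
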